#### Screening

Individuals interested in participation will go through screening through REDCap to determine initial eligibility based on criteria listed above. If potentially eligible, research staff will contact the individual to explain the research protocol, answer questions, and discuss informed consents. Potential subjects interested in participation will be scheduled for a first research visit with research staff. Initial eligibility will be confirmed with direct interview. If eligible, participants will be consented for secondary screening. Secondary screening will consist of baseline assessments and 2 weeks of intervention to assess compliance.

### 6.2.2 Enrollment, Baseline, and/or Randomization Enrollment

Enrollment into the clinical trial will be defined by patient having met all screening criteria and signed the informed consent for participation in the clinical trial

#### Baseline Assessments

For participants who have completed primary screening for eligibility and enrolled for secondary screening, baseline assessments will be performed to measure study outcomes.

- Autonomic tone: We will estimate autonomic tone of participants by standard autonomic testing of cardiovagal and sympathoneuronal functioning including heart rate variability and baroreflex sensitivity. Subjects will have fasted the night before testing, and testing will occur at the same time of the day for each subject to account for temporal variations of autonomic tone.
- Questionnaires: PROMIS Anxiety Scale, Anxiety Sensitivity Index-3 (ASI-3), Beck Anxiety Inventory, Body Vigilance Scale, Panic Disorder Severity Scale, and Perceived Stress Scale-10 (PSS), PROMIS Depression scale, and PANAS-X.
- Catecholamine Profile: Plasma norepinephrine and epinephrine levels will be

measured at baseline in supine and standing positions.

- Current Medications
- Concomitant Interventions

### **Randomization**

Randomization will occur after secondary screening is complete. Treatment assignments will be generated in a 1:1 ratio stratified by gender.

#### **6.2.3 Blinding**

Blinding is summarized in the table below, and described in detail as follows:

1. Participants: Participants will not be able to be blinded to the treatment interventions as this is a behavioral intervention. However, during recruitment, screening, and consent, research staff and mind-body therapists will not state the specific hypothesized function/effect of the treatment interventions- physiological or psychological relaxation. We will describe the intervention as “focused breathing” that is being researched in regards to effects on healthy, and that focused breathing has been shown to improve general well-being. Mind-body therapists have been trained to deliver the protocol without specifying the function of the treatment interventions.
2. Mind-body therapists: Therapists delivering the treatment intervention will not be blinded to the treatment interventions. Therapists will be blinded to primary and secondary outcome measures of stress. Therapists will have access to biometric data regarding fidelity of breathing interventions at home to ensure compliance to the intervention during the study period.
3. Outcome assessors: Research staff collecting physiological and psychological stress data will be blinded to treatment intervention assignments. A research staff member separate from those collecting stress measures will collect data regarding fidelity to breathing interventions.
4. Data analysts/statistician: Data analysts including the statistician will be blinded to treatment assignments until data analyses are complete.
5. Principal investigator: Principal investigator will be blinded to treatment assignments until data analyses are complete.

#### **BLINDING TABLE:**

Stake holder	Intervention group assignment	Primary Mechanistic Outcome Measure (Physiological stress)	Secondary Mechanistic outcome measure (Psychological stress)
Participants	No	Yes	Yes
Instructors	No	Yes	Yes
Outcome Assessors	Yes	No	No
Statistician	Yes	No	No

Principal Investigators	Yes	No	No
--------------------------------	------------	-----------	-----------

#### **6.2.4 Follow-up Visits**

- Once a week in a private office on the Vanderbilt University campus
  - Slow breathing with either exhale > inhale or exhale = inhale
  - Adherence to intervention: Measure subject adherence to study protocol including quality, duration, and breathing goals
  - Adverse events: Document frequency and severity of adverse events during the study
  - Fidelity of breathing by self-report and direct observation by mind-body teachers
- At 6 weeks
  - Autonomic tone
  - Catecholamine Profile
  - Questionnaires: PROMIS Anxiety Scale, Anxiety Sensitivity Index-3 (ASI-3), Beck Anxiety Inventory, Body Vigilance Scale, Panic Disorder Severity Scale, and Perceived Stress Scale-10, PROMIS Depression scale, and PANAS-X.
  - Current Medications
  - Concomitant Interventions
- Two one week periods from weeks 3-6 and 7-12:
  - Fidelity measure using biometric garment- HEXOSKIN

#### **6.2.5 Completion/Final Evaluation**

- At 12 weeks
  - Autonomic tone
  - Catecholamine Profile
  - Questionnaires: PROMIS Anxiety Scale, Anxiety Sensitivity Index-3 (ASI-3), Beck Anxiety Inventory, Body Vigilance Scale, Panic Disorder Severity Scale, and Perceived Stress Scale-10, PROMIS Depression scale and PANAS-X.
  - Current Medications
  - Concomitant Interventions

Participants who discontinue the study intervention early will require no specific evaluations.

The reason for discontinuation will be documented. If research participants no longer want to participate in the research study, we will terminate them from the study. Participants terminated from the study will undergo no further monitoring or follow-up once they have stopped the study intervention.

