## 5. STUDY INTERVENTIONS

### 5.1 Interventions, Administration, and Duration

**Development:** We designed breathing protocols to examine the effect of slow breathing on stress measures among healthy adults. The breathing interventions for this study were developed by [name] in conjunction with an expert panel of 3 mind-body therapists. The breathing protocol uses a well-developed progression of breathing taught in the Krishnamacharya tradition of yoga (Vinyoga).

**Breathing instruction:** Participants will receive 12 weekly private classes taught by a certified mind-body teacher (yoga teachers) specifically trained to deliver the slow breathing protocols. Teachers are specifically instructed not to reveal the goal of the breathing exercises (i.e. relaxation). Each class will be 45 minutes long. The first two weeks of the protocol teaches same basic slow and deep breathing to both treatment arms. The purpose of the first two weeks is to allow all participants an opportunity to become familiar with basic components of deep breathing. Participants will be asked to perform breathing exercises daily in the evening.

Participants will be given written instructions and drawings to guide home practice. During the two weeks for secondary screening, the teacher will assess the subjects' respiratory rate while breathing deeply. Subjects will be eligible only if they achieve a respiratory rate of 8 breaths a minute or less. This is based on principles of pranayama that breath ratios above this respiratory rate are not useful. On the other end of the spectrum, subjects who are already able to breathe very slowly, defined as 3 breaths per minute or less, will not be included. Subjects will only be included who perform the practice 3 or more times a week, based on self-report, during the first two weeks.

To facilitate breathing regulation and standardization between participants, participants will be given an MP3 player with a recorded track that made an audible sound every second (60 Hz). Subjects will be asked to count the length of each breath based on the recording. Subjects demonstrating eligible respiratory rates will proceed to the randomized breathing interventions described below.

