## 7.2 Adverse Events and Serious Adverse Events

Definition - An adverse event (AE) is any untoward medical occurrence in a subject temporally associated with participation in the clinical study or with use of the experimental agent being studied. An adverse finding can include a sign, symptom, abnormal assessment (laboratory test value, vital signs, electrocardiogram finding, etc.) or any combination of these.

A Serious Adverse Event (SAE) is any adverse event that results in one or more of the following outcomes:

- Death
- A life-threatening event

- Inpatient hospitalization or prolongation of existing hospitalization
- A persistent or significant disability/incapacity
- A congenital anomaly or birth defect
- Important medical event based upon appropriate medical judgment

Research staff and mind-body therapists will document and report solicited AEs including physical or psychological discomfort related to anxiety, blood pressure changes, depression, lightheadedness/dizziness, muscle cramps, musculoskeletal injury, or respiration. Unsolicited events will be captured through observation by research staff. Research staff will document unsolicited events and report AEs according to data safety monitoring plan. Events will be documented in the RedCap data entry system including date and time of event which will avoid double capture.

Adverse Reporting: The Independent Monitoring Committee (IMC) will monitor and review adverse events, and toxicities and events that may be related to the intervention.

- a) Non-serious adverse events will be reviewed on a monthly basis by the IMC. The IMC will be notified of serious adverse events within 24 hours of occurrence and reviewed within 48 hours.
- b) Unexpected fatal or life-threatening AEs related to the intervention will be reported to the NCCIH Program Officer within 7 days. Other serious and unexpected AEs related to the intervention will be reported to the NCCIH Program Official within 15 days.
- c) Anticipated or unrelated SAEs will be handled in a less urgent manner but will be reported to the Independent Monitor(s), IRB, NCCIH, and other oversight organizations in accordance with their requirements. In the annual AE summary, the Independent Monitor(s) Report will state that they have reviewed all AE reports.

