## 8. INTERVENTION DISCONTINUATION

The intervention will be discontinued for a participant if: 1) the intervention is associated with an adverse effect for a specific subject i.e. subject does not tolerate the intervention, 2) the subject no longer is interested or willing to receive the intervention or participate in the study, or 3) the subject's healthcare provider no longer recommends that the patient receive the intervention for medical reasons. The IMC and the principal investigator will review cases upon occurrence for discontinuation of intervention.

This study will be stopped prior to its completion if: (1) the interventions are associated with adverse effects that call into question the safety of the intervention, or (2) difficulty in study recruitment or retention will significantly impact the ability to evaluate the study endpoints, or (3) any new information becomes available during the trial that necessitates stopping the trial; or (4) other situations occur that might warrant stopping the trial.

Participants will be followed with their permission if the study is discontinued. The duration of follow-up will be length of the proposed study. We will continue to document adverse events, medications, and vital signs during the follow-up period.

Temporary discontinuation of the treatment may occur if the participants are absent due to travel/vacation, illness including hospitalization, non-compliance, or difficulties with transportation to sessions. Treatment will continue upon return to regularly scheduled sessions. We will continue to document adverse events and medications during temporary discontinuation.

Subjects may withdraw from the study at any time. Investigators may end the participation of the subject if they no longer qualify, have a serious adverse event, or upon request of the DSMB. To withdraw from the study, subjects will notify [name]. At that time, patients will no longer take part in any interventions and no further research data will be collected.

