## 9.3 Definition of Populations

All analyses will be performed as intention-to-treat. Our intent-to-treat population will include all participants who are randomized with baseline assessment and at least one post-randomization assessment.

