Based on our pilot study, we anticipate 20% missingness on post-randomization assessment. Mixed-effects models are robust in the sense that they can include subjects with missing data at one time point (6 week or 12 week) to estimate the effects of interest. We will also perform multiple imputation for missing data to corroborate our findings. Specifically, all the baseline variables and outcome variables will be included in the imputation model, and flexible additive imputation models and predictive mean matching approach will be used to impute missing values. We will use Rubin's method to combine the estimated regression coefficients and variances from the models based on ten imputed complete data sets. A Pearson correlation coefficient between changes in HF HRV and changes in PROMIS Anxiety will be calculated at each post-randomization assessment, for each intervention group or for all the participants respectively, along with 95% confidence interval. In addition, linear regression analysis of HF HRV changes on PROMIS Anxiety changes, age and gender will be conducted.

Per-protocol analysis will be also performed as a sensitivity analysis, and only participants who practice breathing at home at least 3 times a week and achieve prescribed breathing rate and ratio for at least 2 time periods after randomization will be included.

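### Nothing readable in the plan requires week 6 or week 12 outcomes from people who stop the intervention, and no analysis tests whether that loss depends on unseen outcomes.

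*Combined protocol and SAP*

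**What the plan says.** Three rules govern data after someone stops.

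- Section 6.2.5: "Participants who discontinue the study intervention early will require no specific evaluations".
- Section 6.2.5, on people who no longer want to be in the study: "Participants terminated from the study will undergo no further monitoring or follow-up once they have stopped the study intervention".
- Section 8, on withdrawal: "At that time, patients will no longer take part in any interventions and no further research data will be collected".

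Section 8 lists unwillingness to continue as one reason for stopping the intervention. It lists intolerance separately: "the intervention is associated with an adverse effect for a specific subject i.e. subject does not tolerate the intervention". Section 7.2 has staff record "solicited AEs including physical or psychological discomfort related to anxiety", and PROMIS Anxiety is the Aim 2 primary outcome.

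On analysis, section 9.3 states: "Our intent-to-treat population will include all participants who are randomized with baseline assessment and at least one post-randomization assessment". Section 9.6 states: "Based on our pilot study, we anticipate 20% missingness on post-randomization assessment". It plans a t-test on change to week 12, a mixed model on the 6- and 12-week changes, multiple imputation with ten data sets, and a per-protocol analysis as the sensitivity analysis.

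**The concern.** An intention-to-treat comparison needs outcomes from randomised people whether or not they keep practising. If people who stop are not measured, the comparison describes those who stayed.

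Loss that differs by arm is not in itself a bias. For the t-test, bias needs stoppers' outcomes to differ from those of similar people who stay, together with either unequal loss or loss of the benefit among stoppers. A link between stopping and outcome is plausible here, since intolerance is a listed reason for stopping and anxiety is both a solicited adverse event and a primary outcome.

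The run-in, with its requirement of at least three practices a week, lowers the risk. It cannot screen for intolerance of the assigned ratio, because "The first two weeks of the protocol teaches same basic slow and deep breathing to both treatment arms" and the ratios begin only after randomisation.

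Enrolling 50 per arm protects precision and does nothing about this bias.

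**Working it through.** **Do the documents close the gap?** Other text on follow-up does not.

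- Section 8 provides for follow-up if the whole study is discontinued (by permission; adverse events, medications, vital signs) and during temporary discontinuation (adverse events, medications). Neither covers outcomes.
- The Précis and sections 6.2.4 and 6.2.5 give the 6- and 12-week schedule without saying that it applies after stopping.
- The section 6.1 table and the consent forms could not be read.

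**Do the analyses test it?** The mixed model and the imputation as described assume missing at random. The per-protocol set keeps adherent participants only. No analysis varies the assumption.

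**The plan's own figure.** For a difference of 265, SD 406 and two-sided 0.05, t-test power at 38 per arm is 80.2%, as section 9.2 states. Dropout inflation gives 38/0.8 = 47.5, which the plan rounds up to 50. The sample size is not in dispute.

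**Inputs for the illustrations.** From section 9.2: difference 265, SD 406, PROMIS Anxiety difference 5.2, pilot 6-week effect 173 − 58 = 115, loss 20%. Assumed: the split of loss by arm, the stoppers' deficit (0.5 SD = 203), and the correlation between visits (r = 0.6, range 0.4 to 0.8). No repair by baseline, age or gender is counted, and multiple imputation is not modelled.

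**1. Equal loss, benefit lost.** Let p be the share of permanent stoppers and f the fraction of benefit they keep. The difference across all randomised is 265 × (1 − p(1 − f)).

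| p = 0.2 | f = 0 | f = 0.5 | f = 1 |
|---|---|---|---|
| HF HRV | 212 | 238.5 | 265 |
| PROMIS Anxiety | 4.16 | 4.68 | 5.2 |
| t-test overstatement, HF HRV | 53 | 26.5 | 0 |

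The random-intercept model recovers only what already shows at week 6. With f = 0 and every stopper having week-6 data that show the loss, it overstates by 53 − r × 0.2 × 115 = 39.2 at r = 0.6 (43.8 at 0.4, 34.6 at 0.8). If no stopper has week-6 data, or the benefit goes only after week 6, it overstates by the full 53.

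The 20% is general missingness. If only half is permanent stopping (p = 0.1), f = 0 gives 265 × 0.9 = 238.5.

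**2. Stoppers 0.5 SD worse in both arms.** Let p1 and p0 be the losses in the two arms. The t-test bias is (p1 − p0) × 203. If a share g of stoppers have week-6 data, s = gp/(1 − p + gp) in each arm, and the mixed-model bias is (p1 − p0) × 203 − r × (s1 − s0) × 203.

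| Loss by arm | t-test | Mixed, g = 1 | Mixed, g = 0.5 | Mixed, g = 0 |
|---|---|---|---|---|
| 20% / 20% | 0 | 0 | 0 | 0 |
| 25% / 15% | 20.3 | 8.1 | 12.8 | 20.3 |
| 30% / 10% | 40.6 | 16.2 | 25.5 | 40.6 |

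Mixed-model columns use r = 0.6. For 30%/10% with g = 1, r = 0.4 and 0.8 give 24.4 and 8.1. A deficit that arises only after week 6 leaves the full 40.6 for every g and r. All signs reverse if the loss pattern reverses.

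A simulation of the random-intercept fit (150,000 per arm, r = 0.6) gave 15.8, 25.3 and 40.6 for the 30%/10% row at g = 1, 0.5 and 0. With no deficit the bias was within Monte Carlo error of zero.

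The standard error is 406 × √(1/35 + 1/45) = 91.5, so a bias of 40.6 raises the t-test's type I error from 5% to about 7.3%. If half of the 30%/10% loss is stoppers, the bias is 0.10 × 203 = 20.3.

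**3. What partial recovery buys, t-test.** If a share h of stoppers attend week 12, the estimate in case 1 (f = 0) is 265 × (1 − 0.2h/(0.8 + 0.2h)).

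| h | Estimate (target 212) | Overstatement | 30%/10% bias |
|---|---|---|---|
| 0 | 265 | 25% | 40.6 |
| 0.25 | 249.4 | 17.6% | 26.4 |
| 0.5 | 235.6 | 11.1% | 15.5 |

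**The case against.** The key sentence in section 6.2.5 may mean only that no extra exit visit is needed. The sentence on ending follow-up concerns people leaving the study, a narrower group than those who stop practising. The Précis states the 6- and 12-week assessments without exception, and section 6.2.1 counts two research visits apart from the sessions. This reading is possible, and nothing bars assessing a stopper who stays. But no readable text requires it, and an ambiguous rule gives staff no reason to pursue those visits.

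The route through intolerance may also be narrow. Related non-serious events lead to modification of the breathing protocol, and absence or non-compliance is handled as temporary discontinuation. That reduces the number of such stoppers without removing the group that section 8 names.

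The sizes are assumptions. The pilot randomised 21 and reports HF HRV change for 18, about 14% without data and no reasons given. A 30%/10% split would be 15 against 5 of 50 (Fisher p = 0.02), and nothing in the documents predicts it. Biases of 20 and 41 are about 0.2 and 0.45 standard errors. Imputation using all outcome scales could repair more than is counted here. These points stand: they limit what can be said about size, but do not supply an analysis that tests the assumption.

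The analysis-set wording is mainly a label. Excluding people with no later visit changes neither the t-test nor the change-score mixed model. It matters for the imputation and for the name given to the set.

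**Conclusion.** The concern holds and should be fixed, with medium confidence. As written, the plan can lose outcomes that its intention-to-treat comparison needs, and no planned analysis examines departure from missing at random. The bias is of unknown size and sign and could be zero. In the scenarios shown it runs from 0 to 53 HF HRV units, or 0 to 20% of the planned 265. That range depends on the assumed loss pattern, deficit and visit correlation, and on how much of the 20% missingness is permanent stopping. Outcomes not collected at the time cannot be recovered later.

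**What to change.** - In sections 6.2.5 and 8, separate stopping the intervention from withdrawing consent for data.
- Ask people who stop but still agree to attend the week 6 and week 12 assessments already scheduled: at minimum the online PROMIS Anxiety, and HF HRV where they agree.
- Analyse all randomised participants as assigned, with imputation covering those with no later visit, or call the present set modified intention-to-treat.
- Add a sensitivity analysis that shifts stoppers' imputed values separately by arm, for example over 0 to 0.5 SD, and state that arm is in the imputation model.

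The cost is protocol and consent wording plus one analysis, with no new visits. Section 10.1 already allows questionnaires to be completed online at home, so retention effort there is small. It is larger for HF HRV, which needs fasted on-site testing. People who withdraw consent for data remain unmeasured, so the share recovered is unknown.

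The estimate may become smaller. If stoppers keep no benefit, power with all 50 per arm measured is 73% for 212, against 82% for 265 with 40 per arm.

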### **7. SAFETY ASSESSMENTS**

This research protocol employs breathing techniques among healthy adults that involves low risk to human subjects. Subjects will be frequently asked about symptoms relating to adverse events or discomfort. While expected to be very

rare, possible serious adverse events related to breathing practices may include:

- cerebrovascular accident
- life threatening arrhythmias (e.g. ventricular tachycardia)
- myocardial infarction
- sudden death

Non-serious adverse events from breathing techniques may include

- acute symptomatic episodes from problems with blood pressure,
- anxiety
- lightheadedness/dizziness
- muscle cramps,
- musculoskeletal injury,
- respiration (shortness of breath or respiratory discomfort),

Other theoretical risks from study tests include:

- local risks associated with venipuncture blood draws

There may be risks and side effects that are currently unknown and/or unanticipated.

*Because these risks are unlikely given previous behavioral studies mind-body therapy practices, and most are inherent risks within the general population and not solely due to study procedures, the potential benefits of this study to the individual and society reasonably outweigh the risks.*

